An important limitation of the CAE-L pilots is that they excluded individuals with BD. The pilot studies combined LAI + CAE data suggested that patients with schizoaffective disorder (N=44) did just as well as those with schizophrenia (N=16) with respect to adherence, symptom and functional outcomes (Levin et al., 2017). Combining Maintena with a practical method of adherence support has potential to enhance uptake and optimize enduring adherence to medication in patients with BD.

Project Design:

Overview: 6-month, prospective, trial testing the effects of Maintena augmented with CAE in 30 poorly adherence patients with BD. After a 2-month study start-up period, patients will be enrolled over a 16 month enrollment period (months 2-18). The targeted enrollment of approximately 2 participants/month is reasonable given previous recruitment with the CAE + LAI pilots. Primary outcomes will be change from baseline in adherence as identified by the Tablet Routines Questionnaire (TRQ) and injection frequency at the 6-month time-point. We will also evaluate changes in secondary outcomes, including BD symptoms (BPRS), depressive and global psychopathology symptoms, functional status, and adherence attitudes. Additional exploratory assessments will include health resource use, adherence barriers, substance use and neurocognition. Outcome measures will be assessed at Screening, Baseline, and Weeks 4- 24 as noted in Table 2/Study Schedule of Events. Because the study design will be nearly identical to the 2 previously conducted CAE + LAI pilots, it will be possible to compare primary and secondary outcomes of this study of individuals with BD to individuals with schizophrenia/schizoaffective disorder. The study will be operationalized in 4 specific Aims:

Aim 1: Test whether combined Maintena + CAE (Maintena +) is associated with improved treatment adherence

[figure not shown]
Hypothesis 1: At 6-month follow-up, poorly adherent BD patients receiving Maintena + will have significant improvement in medication adherence as measured by the TRQ.

Hypothesis 2: At 6-month follow-up we also expect that mean LAI adherence as measured by injection frequency will meet or exceed 80%. The 80% threshold is widely viewed in the treatment adherence literature as an “acceptable” degree of adherence.

Aim 2: Test whether Maintena + is associated with reduction in BD symptoms, improved functioning and better treatment attitudes

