4. Recruitment will be done by oral request to patients coming for regularly scheduled clinic visits at UHCMC or area CMHCs. Requests for participation may be initiated by a clinic staff member, by a research associate on site, or in some cases may be initiated by patients themselves.
5. Patients with BD will be identified from the UHCMC electronic medical record and using an IRB-approved process, be invited to participate in study screening.
6. Patients may also be recruited under the MHERP/NBOC Prescreen protocol.

All individuals with BD who are referred will be considered for possible inclusion in the study. A Screening Form for each patient will be completed regardless of whether the patient is ultimately enrolled. The form will detail reasons for exclusion, allowing an estimate of sample generalizability. Patients recruited in response to an IRB-approved recruitment method may be prescreened under the IRB-approved protocol, "Prescreening and Recruitment for the Mental Health Effectiveness Research Program and Neurological and Behavioral Outcomes Center" (MHERP/NBOC Prescreen) [IRB # 03-10-09].

The study PI ([name], Professor of Psychiatry at CWRU and UHCMC) will oversee and be responsible for all aspects of the study including study regulatory matters, human subjects requirements, study implementation, study staff supervision, and data collection, analysis and reporting. Study Co-investigators will assist the study PI in study referral, clinical and safety monitoring, training and oversight of interventionists, and participant retention. The PI has successfully conducted multiple treatment adherence studies over the last decade and has an extensive track-record of robust recruitment of non-adherent patients with BD and other serious mental illnesses. Diagnosis will be confirmed with a standardized brief interview commonly utilized in clinical trials, the Mini International Neuropsychiatric Inventory (MINI). In order to facilitate a relative comparison of BD patient response to outcomes in this study vs. recently completed pilot trials, we will deliberately recruit individuals with similar study entry level symptom severity. In the proposal trial, study entry Brief Psychiatric Symptom Rating Scale (BPRS) scores will not be below 1 standard deviation of the mean BPRS in pilot work.

Inclusion Criteria:

1. Individuals age 18 and older with BD Type 1 or 2 as confirmed by the Mini International Psychiatric Inventory (MINI).

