2. Known to have medication treatment adherence problems as identified by the Treatment Routines Questionnaire (TRQ, 20% or more missed medications in past week or past month)
3. Screening BPRS score of ≥ 36
4. Ability to be rated on psychiatric rating scales.
5. Willingness to take LAI
6. Currently in treatment or scheduled to receive treatment at a Community Mental Health Clinic (CMHC) or other clinical setting able to provide mental health care during and after study participation
7. Able to provide written, informed consent to study participation.

Exclusion Criteria:

1. Individuals on LAI immediately prior to study enrollment.
2. Individuals with known intolerance or resistance to either oral aripiprazole or LAI formulation of aripiprazole
3. Prior or current treatment with clozapine
4. Medical condition or illness, which in the opinion of the research psychiatrist, would interfere with the patient's ability to participate in the trial
5. Physical dependence on substances (alcohol or illicit drugs) likely to lead to withdrawal reaction during the course of the study in the clinical opinion of the treated research psychiatrist
6. Immediate risk of harm to self or others
7. Female who is currently pregnant or breastfeeding

Study Medication: Medication dosing will follow recommendations in the Maintena package insert. For patients who have never received aripiprazole, there will be a brief oral tolerance testing (OTT) of up to 14 days. Individuals who tolerate OTT will then receive 400 mg of Maintena administered IM in the gluteal or deltoid location, and oral Abilify will continue for an additional 14 days, after which oral medication will be discontinued. After the initial IM injection, individuals will continue to receive injections of Maintena every month for a total of 6 months. The standard dosage of 400 mg IM will be administered in this maintenance treatment phase although clinicians may administer a lower dosage of 300 mg IM depending on clinical response.

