Sample Size and Power: We propose to enroll 30 individuals with BD who receive Maintena +. Based on our prior studies (Sajatovic 2012a, Sajatovic 2012b), we conservatively assume 20% of participants will discontinue study participation during the 24 week study period and that the effect size of CAE-L will be similar to that of CAE-L in prior studies (effect size $d=.60$). Type I error level of 0.05 will be adopted for all tests.

The primary outcomes measure will be change in adherence behavior and the mean LAI injection frequency at 6-months. Adherence rates will be calculated for TRQ in the following manner: the number of days with a missed dose will be divided by the number of days in the time period and then multiplied by 100. Adherence rates will be calculated for both the week and the month prior to assessment visit and for the study period. Given a sample size of 30 subjects with 20% attrition and two-sided Type I error of 0.05, for paired t-tests we will have power of 0.80 for effect sizes of at least 0.597. For correlations, power of 0.80 is achieved for a two-sided test of correlation being zero when the magnitude of correlation is at least 0.51. Hence, there is sufficient power to detect moderate level mean differences and correlation values. For the assessment of mean injection frequency, suppose 6 prescribed injections in 6 months, with a standard deviation of 1.2 (20% of prescribed injections). Then, if a sample mean of 5.28 or higher is observed (88%), a 95% two-sided confidence interval will not contain 4.8, the 80% threshold, This would provide evidence that the percentage of injection frequency is higher than 80%. Note that adherence levels of 80% or higher are widely considered to be "acceptable" adherence in the research literature. The mean LAI injection frequency in our previous pilot work involving LAI + CAE in homeless patients with schizophrenia exceeded 90% of prescribed injections at 6-month follow-up. We thus expect to statistically establish that the mean LAI injection frequency in this bipolar sample who are not homeless is above the 80% threshold.

Data analyses will be performed using the Statistical Analysis System (SAS) (SAS Institute, Cary, NC, 2002).. For Aim 1, change in TRQ from baseline to 24 weeks will be assessed with a paired t-test or Wilcoxon signed rank test. For mean LAI injection frequency, we will construct 95% confidence intervals. Exploratory longitudinal

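### The 88% cut-off for injection frequency rests on an unsourced SD of 20%, while the pilot row behind the expected mean shows a spread near 30%, so the stated expectation of success is optimistic

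*Combined protocol and SAP*

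**What the plan says.** Injection frequency at 6 months is one of two primary outcomes (Project Design; Sample Size and Power). Hypothesis 2 under Aim 1 expects that "mean LAI adherence as measured by injection frequency will meet or exceed 80" percent.

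The Sample Size and Power section plans this outcome in three steps:

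- It assumes a spread: "suppose 6 prescribed injections in 6 months, with a standard deviation of 1.2 (20% of prescribed injections". No source is given.
- It states the consequence: "if a sample mean of 5.28 or higher is observed (88%), a 95% two-sided confidence interval will not contain 4.8, the 80% threshold".
- It recalls that the pilots' mean "exceeded 90% of prescribed injections at 6-month follow-up" and concludes: "We thus expect to statistically establish that the mean LAI injection frequency" is above the threshold in this sample, which it describes as not homeless.

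Table 1 (Background) reports injection frequency in the combined pilots as 86.1 (32.8) at week 13 and 90.5 (30.1) at week 25, with N = 50. The Adherence paragraph under Measures and Schedule of Events says that the pilots' injection benchmarks will be reused, with an injection counted if given within 7 days of schedule. The planned analysis is a 95% confidence interval for the mean.

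**The concern.** The plan takes its expected mean from the pilots but not the spread printed beside that mean, and it does not say why a spread of 20% should apply. The width of the interval, and so the cut-off, is proportional to the SD. If the true SD is well above 20%, a result as good as the pilots' could fail to exclude 80%, although the plan tells its reader to expect success. The section gives power for the paired t-tests and the correlations but none for this outcome, so nothing else in the plan shows the reader how likely that is.

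**Working it through.** **Inputs.** Enrolled 30, attrition 20%, so n = 24; planned SD 20% (1.2 of 6); threshold 80% (4.8 of 6). All are from Sample Size and Power. The pilot mean of 90.5% and spread of 30.1 are from Table 1.

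**Are the brackets in Table 1 SDs?** The table does not label them. Study Population says entry BPRS "scores will not be below 1 standard deviation of the mean BPRS in pilot work", and the inclusion criterion is "Screening BPRS score of ≥ 36". Table 1 gives baseline BPRS as 44.1 (8.3), and 44.1 − 8.3 = 35.8, which rounds to 36. The brackets behave as SDs.

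**Reproducing the plan's figure.** Cut-off = 80 + c × SD/√n. With c = 1.96, 80 + 1.96 × 20/√24 = 80 + 8.0 = 88.0%, or 5.28 of 6. The match is exact, so the plan used a normal interval with 24 patients.

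**t interval at the plan's SD.** With 23 df, c = 2.069, and 80 + 2.069 × 20/√24 = 88.4%, or 5.31 of 6.

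**Larger SD.** At SD 25%: 80 + 1.96 × 25/√24 = 90.0% (normal), 80 + 2.069 × 25/√24 = 90.6% (t).

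**Ceiling.** On a 0–100% scale the SD at mean m cannot exceed √(m(100 − m)). At 90.5% this is √(90.5 × 9.5) = 29.3% (sample SD with n = 24: 29.3 × √(24/23) = 29.95%). The limit falls as the mean rises. Solving m = 80 + c × √(m(100 − m) × 24/23)/√24 gives the highest attainable cut-off: 91.4% (normal) or 91.8% (t).

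**Largest SD at which an observed 90.5% still excludes 80%.** (90.5 − 80) × √24/c = 10.5 × 4.899/1.96 = 26.2% (normal), or 10.5 × 4.899/2.069 = 24.9% (t).

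**Chance of excluding 80% if the true mean is 90.5%, n = 24.** The normal column is 1 − Φ(1.96 − 10.5√24/SD). The t column uses the noncentral t with 23 df. The last column simulates counts out of 6 (beta-binomial, 200,000 trials) and applies each interval.

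| SD | Normal theory | t theory | Bounded simulation (normal / t interval) |
|---|---|---|---|
| 20% | 73% | 69% | 68% / 66% |
| 25% | 54% | 50% | 55% / 52% |
| 29% | 43% | 40% | 57% / 35% |

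The simulated results spread at 29% because the data are then nearly all-or-nothing. If two of 24 patients score zero and the rest 100%, the mean is 91.7% and the SD 28.2%. The lower limit is 91.7 − 1.96 × 28.2/√24 = 80.4% (normal) but 91.7 − 2.069 × 28.2/√24 = 79.8% (t). One patient, or the choice of interval, decides the outcome.

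**The case against.** A reader might put 30.1% into the plan's formula and conclude that 92% is needed and that the chance of success is 40%. The documents do not support that. With 24 patients and a mean of 92%, the sample SD cannot exceed √(92 × 8 × 24/23) = 27.7%, so such a sample cannot occur. 30.1% is an upper bound, not a planning value.

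The row may also not be the planned variable. A yes/no variable with 19 of 21 positive gives exactly 90.5 (30.1), although the table lists N = 50 and the documents do not settle the matter. The plan uses a count out of 6 per patient. Averaging six yes/no events, each with SD 29.3%, gives 20% at a within-patient correlation of 0.36: 29.3 × √((1 + 5 × 0.36)/6) = 20.0%. So 20% need not contradict Table 1.

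Completers may also vary less. If each of the 24 has at least 2 of 6 injections on time, the largest SD at a mean of 90.5% is √(9.5 × 57.2 × 24/23) = 23.8%, and 90.5% then excludes 80%. With at least 3 of 6 it is √(9.5 × 40.5 × 24/23) = 20.0%. If dropouts are kept and supply the spread, n is 30, and at SD 29.3% the normal lower limit is 90.5 − 1.96 × 29.3/√30 = 80.02%, just clear (the t interval is not).

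Finally, the sentence is conditional, no sample size or decision rule depends on it, and the planned analysis is already a confidence interval.

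These points rule out 30.1% as an input and show that a smaller SD is possible. They do not supply the missing reason for 20%. The only contrast the plan draws is housing status, and the eligibility criteria do not mention housing. If the row is not the planned measure, its mean cannot support the expectation either. Even at SD 20%, the chance of success is below the 80% power quoted for the paired t-tests.

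**Conclusion.** The concern holds as a planning weakness that should be corrected. The 88% cut-off is the most favourable end of a plausible range: 88.4% to about 91.8% with a t interval. A repeat of the pilots' mean meets the criterion only if the SD is below about 25–26%. The chance of success is about 66–73% at SD 20%, 50–55% at SD 25% and 35–57% near 29%. None of these supports a plain statement that success is expected.

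This rests on four assumptions: a true mean of 90.5%, 24 analysed patients, a measure bounded at 0–100%, and an SD between 20% and about 29%. Table 1 does not say how its row was calculated.

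A reader might also infer that the analysis is invalid or biased. It is not, because the final interval uses the observed SD. The power statement for TRQ is unaffected.

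**What to change.** In Sample Size and Power:

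1. Give a reason or source for the SD of 20%, or show results for 20–29% and say how the Table 1 row was calculated.
2. Replace the single 88% figure with t-interval cut-offs for 24 patients: about 88.4% at SD 20%, 90.6% at SD 25%, and at most about 91.8% on a bounded measure.
3. Replace the sentence expecting statistical success with the range of chances at a true mean of 90.5%: about 66–73%, 50–55% and 35–57% at SD 20%, 25% and about 29%. Do not print one chance, an SD of 30.1% or a 92% requirement.

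This changes text only and needs no new patients, visits or data. The cost is a less favourable stated expectation for Hypothesis 2.

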A 6-month, prospective, randomized controlled trial (RCT) of CAE vs. an educational control is being conducted in 184 poorly adherent adults with BD. To enhance generalizability, CAE is delivered by social workers. Interim RCT outcomes (CAE N=24, EDU N=26) show that CAE is associated with improved adherence as measured by the Tablet Routines Questionnaire (TRQ mean change=46.0, SD=38.7) compared to an educational control (EDU) (TRQ mean change=17.3, SD=40.3, p=.017). Six-month MEMS adherence change was also greater with CAE (mean change 45.7, SD 40.6) compared to EDU (mean change 15.9 (SD 39.9), p=.015). Effect sizes for CAE in both TRQ and MEMS are approximately 0.75, comparing favorably with effect size for response to BD medications.

Combining LAI + CAE dramatically improves adherence, symptoms and functional outcomes in people with schizophrenia and schizoaffective disorder: These investigators tested a combined LAI + CAE approach (CAE-L) in 2 preliminary studies. CAE-L Study 1 (Sajatovic 2013) enrolled 30 homeless or recently homeless individuals with schizoaffective or schizophrenia. The LAI used was haloperidol decanoate. Primary outcomes were TRQ and housing status. Secondary outcomes included psychiatric symptoms and functional status. Mean sample age was 41.8 years with a high proportion of minorities and single/never married individuals. CAE-L was associated with substantial improvement in concomitant orally prescribed medication, which changed from missing 46% of prescribed medication at study enrollment to only 10% of prescribed medication at study end. Mean proportion of time in sub-optimal housing went from 56% in the 6 months prior to study enrollment to 41% in the first 3 months of the study and 14% in the last 3 months of the study. There were also significant improvements in psychiatric symptoms and functional status.

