In CAE-L Study 2 (Sajatovic 2016), CAE-L was delivered by social workers and used the LAI paliperidone palmitate. This 6-month prospective, uncontrolled trial of CAE-L in 30 recently homeless individuals with schizophrenia or schizoaffective disorder assessed medication adherence using the TRQ and injection frequency. Psychiatric symptoms were measured with the Positive and Negative Syndrome Scale (PANSS), Brief Psychiatric Rating Scale (BPRS) and global psychopathology. Standardized measures of extrapyramidal symptoms included the Simpson Angus Scale (SAS), the Barnes Akathisia Scale (BAS), and the Extrapyramidal Symptoms Scale-Abbreviated version (ESRS). Social functioning was assessed via the Social and Occupational Functioning Assessment Scale (SOFAS). Mean age of the sample was 43.6 years, mainly minorities, single/never married with a mean of 11.55 years of education. Baseline rate of substance abuse within the past year was 40.0%. Four individuals (13.3%) terminated the study prematurely. CAE + LAI was associated with improved adherence as measured by the TRQ (p=.02). There were significant improvements in PANSS (p <.01), BPRS (p<.001), CGI (p =.003) and SOFAS (p=.005). There were no significant mean changes on SAS, BAS, ESRS-A. The CAE-L studies combined dataset (Table 1)(Sajatovic M 2016) shows changes in medication adherence, psychiatric symptoms, global psychopathology and social functioning. Adherence with regular LAI injections was excellent, with > 90% receiving injections within 1 week of regularly scheduled treatment.

Table 1: Combined data of CAE-L for 60 poorly adherent patients with schizoaffective disorder/schizophrenia

Variable	Screen	Baseline	Wk 13	Wk 25	N	Statistic
TRQ Mean						
Past Week	50.4% (32.4)	26.7% (29.3)	16.8% (29.5)	17.1% (30.6)	26	.001
Past Month	45.2% (33.6)	32.5% (30.4)	16.2% (24.9)	13.8% (23.2)	25	.002
Injection Frequency	-	-	86.1 (32.8)	90.5 (30.1)	50	.060
BPRS Mean	-	44.1 (8.3)	33.9 (7.9)	30.8 (8.3)	41	< .001
PANSS Mean						
Positive Symptoms Scale	-	16.7 (6.3)	-	12.4 (5.8)	36	.001
Negative Symptoms Scale	-	28.5 (10.9)	-	20.8 (7.9)	35	<.001
Composite Scale (Pos - Neg)	-	14.9 (10.3)	-	7.8 (8.2)	36	<.001
General Psychopathology Scale	-	19.9 (18.9)	-	9.8 (14.1)	36	<.001
CGI Severity Mean	-	4.6 (0.9)	3.4 (0.7)	3.1 (0.8)	38	<.001
SOFAS Mean	-	51.1 (8.1)	-	61.3 (9.7)	40	<.001

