Concomitant Medications As it is known that multi-drug maintenance treatment is the rule rather than the exception in BD, and in order to increase generalizability of study findings, patients will be permitted to continue other psychotropic maintenance treatments. Maintenance treatments are defined as traditional mood stabilizing drugs (such as lithium, valproate or lamotrigine), or antidepressants that have been continued for at least one month at a stable dosage. Dosing on other concomitant treatments is required to remain unchanged for the duration of the study. Medications for side effects (for example, benztropine) may be given at the discretion of the treating psychiatrist. Hypnotic drugs for insomnia/sleep that have been prescribed for at least 30 days may continue to be administered daily (for example zolpidem) at the same dosage.

CAE: The CAE intervention will be modeled and delivered using procedures used in the CAE + LAI pilots. CAE will be delivered by a trained social worker to optimize generalizability. CAE session will be delivered on the same day (either immediately before or immediately after Maintena injection). Supervision will be conducted with a PhD psychologist who helped develop CAE and training will be reinforced as needed.

Measures and Schedule of Events: Table 2 shows the assessment measures, timeline the measures are given, and other specific procedures in the study. Demographic and clinical variables measured at baseline will include age, gender, race/ethnicity, living situation, cumulative medical burden and socioeconomic status at baseline. As in 2 previous successful studies using the medication + adherence support approach in high-risk SMI (Sajatovic 2012a, Sajatovic 2012b) the primary outcome measure will be adherence as assessed via the Tablet Routines Questionnaire (TRQ)

Adherence: A number of investigators have defined "good" adherence in serious mental illness as missing no more than 20% of medication (Gilmer 2004, Valenstein 2004). In previous studies, we demonstrated that this cut-off is sufficient to detect adherence change over time with CAE (Levin 2014, Velligan 2010). Adherence to Maintena will be assessed using the same injection frequency benchmarks used in the previous CAE-L studies (injection is counted as "adherent" if administered within 7 days of when it is scheduled to be administered).

Barriers assessed include BD knowledge, communication with clinicians, medication routines, and substance use.

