Safety evaluations will include baseline and Week 24/End-of-study basic laboratory evaluations (comprehensive metabolic panel, lipid profile, CBC with differential) and pregnancy testing for women. EKG will be conducted at baseline, week 4 and Week 24/End-of-study. Patient vital signs and weight will be collected at each study visit (baseline/V1, V2, V3, V4, V5, V6, V7, V8). Standardized measures of involuntary movements/ extrapyramidal symptoms will be assessed with the Simpson Angus Scale (SAS), the Barnes Akathisia Scale (BAS), the Abnormal Involuntary Movement Scale (AIMS) and the Extrapyramidal Symptoms Scale-Abbreviated version (ESRS-A). Finally, reported side effects will also be evaluated at each study visit using a form derived from the previous CAE-L studies.

Table 2: Measures and Study Schedule of Events

Visit	Screen	BL/ V1	V2	V3	V4	V5	V6	V7
Timing [†]	-14 d to -1d	0 W	4W	8W	12W	16W	20W	24W
Informed consent	X							
Inclusion/Exclusion	X							
Adherence Behavior: TRQ LAI Injection Frequency*	X	X	X	X	X	X	X	X
Non-psychotropic drug TRQ	X				X			X
MINI	X							
CAE module allocation and assessment of Adherence barriers	X							X
Physician Exam and interview	X							X
Demographics, medical burden	X							
Laboratory testing	X				X			X
EKG	X		X					X
Adherence Attitudes: DAI, AMSQ		X			X			X
Symptoms: BPRS, YMRS, MADRS, CGI	X†	X			X			X
Functioning: SOFAS, GAF		X						X
Health resource use		X						X
Alcohol/Substance Use: AUDIT, DAST-10		X			X			X
Trails A & B, Animal Fluency	X							X
Weight and vitals		X	X	X	X	X	X	X
Reported Side Effects		X	X	X	X	X	X	X
Extrapyramidal symptoms: AIMS**, SAS, BAS, ESRS-A	X	X	X	X	X	X	X	X
Patient Satisfaction					X			X
Research Clinician assessment		X	X	X	X	X	X	X
CAE sessions		X	X	X	X	X	X	X
Oral aripiprazole Dispensing***	X	X						
LAI Injection		X	X	X	X	X	X	X

[†]Timing of visits is approximate.

* LAI Injection frequency will be calculated at weeks 12 & 24.

** AIMS will only be administered at BL and W24/Term

*** Dispensing of oral medication is patient specific and may include a 14-day oral tolerability test prior to first LAI injection, or dispensing of anti-side effect medications.

† BRPS will be the only symptom evaluated at screen

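### Does Aim 1 leave open whether the Screen or the BL/V1 TRQ value is the baseline, in a way that could decide the result?

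*Combined protocol and SAP*

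**What the plan says.** Under Data Management & Analyses, the Aim 1 test is set out as "For Aim 1, change in TRQ from baseline to 24 weeks will be assessed with a paired t-test or Wilcoxon signed rank test". Table 2 has one column for Screen (day -14 to day -1) and another for BL/V1 (week 0). Its row "Adherence Behavior: TRQ LAI Injection Frequency" is marked in both and at every later visit. TRQ is also an entry criterion: patients must report "20% or more missed medications in past week or past month".

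The Sample Size and Power section expects that "the effect size of CAE-L will be similar to that of CAE-L in prior studies", taken as d = 0.60. It gives a minimum detectable effect of 0.597 for the paired t-test at 80% power, with 30 enrolled and 20% attrition. It does not say which pilot contrast or recall window the 0.60 comes from. TRQ is to be calculated for the past week, the past month and the study period, and none is named as primary.

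The pilot figures are in "Table 1: Combined data of CAE-L for 60 poorly adherent patients with schizoaffective disorder/schizophrenia", which has separate Screen and Baseline columns for TRQ.

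**The concern.** The word baseline is used loosely elsewhere. The Safety Evaluations section says "EKG will be conducted at baseline, week 4 and Week 24/End-of-study", but Table 2 marks the EKG at Screen and not at BL/V1. The Measures section says "Demographic and clinical variables measured at baseline will include age, gender, race/ethnicity, living situation, cumulative medical burden", and Table 2 again places demographics and medical burden at Screen. Background describes CAE-L Study 1 by its oral-medication adherence, "which changed from missing 46% of prescribed medication at study enrollment to only 10% of prescribed medication at study end". That 46% is close to the combined Screen values in Table 1 (45.2% and 50.4%) and far from the Baseline values (32.5% and 26.7%). A reader could conclude that the team habitually measures change from Screen.

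The stakes come from selecting on TRQ. A value used to select poorly adherent patients tends to improve on re-measurement, and this single-arm design has no concurrent control to absorb that. The first CAE session and injection are at BL/V1, so neither can explain a fall between Screen and BL/V1. If Screen were the start, Aim 1 could be met largely on change that preceded treatment. Aim 3, which compares studies by effect size, could mistake unmatched starting visits for a difference between diagnoses.

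**Working it through.** **The plan's own figure.** Completers: 30 × 0.8 = 24. Paired t-test, 23 df, two-sided alpha 0.05, noncentral t: power at d = 0.597 is 0.7998. The stated figure is reproduced.

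**Inputs from Table 1, mean % missed (SD)**

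| Window | Screen | Baseline | Wk 25 | N |
|---|---|---|---|---|
| Past week | 50.4 (32.4) | 26.7 (29.3) | 17.1 (30.6) | 26 |
| Past month | 45.2 (33.6) | 32.5 (30.4) | 13.8 (23.2) | 25 |

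**Share of the fall before Baseline**

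- Past week: 50.4 − 26.7 = 23.7; 26.7 − 17.1 = 9.6; total 33.3; 23.7/33.3 = 0.71.
- Past month: 45.2 − 32.5 = 12.7; 32.5 − 13.8 = 18.7; total 31.4; 12.7/31.4 = 0.40.

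**Effect of the starting visit with 24 completers.** SD of change = √(s₁² + s₂² − 2·r·s₁·s₂); d = mean change / SD of change; t = d·√24. The within-patient correlation r is not in the documents, so it is an assumption shown over a range. Example, past week from Baseline at r = 0.5: √(29.3² + 30.6² − 29.3 × 30.6) = 30.0; d = 9.6/30.0 = 0.32; t = 1.57; p = 0.13.

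| Window and start | r | d | Power | p at the pilot means |
|---|---|---|---|---|
| Week, Baseline | 0 | 0.23 | 0.19 | 0.28 |
| | 0.5 | 0.32 | 0.32 | 0.13 |
| | 0.7 | 0.41 | 0.49 | 0.055 |
| Week, Screen | 0 | 0.75 | 0.94 | 0.0013 |
| | 0.5 | 1.06 | >0.99 | <0.001 |
| Month, Baseline | 0 | 0.49 | 0.63 | 0.025 |
| | 0.5 | 0.68 | 0.89 | 0.003 |
| Month, Screen | 0 | 0.77 | 0.95 | 0.001 |
| | 0.5 | 1.05 | >0.99 | <0.001 |

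For the past week from Baseline, p falls below 0.05 once r exceeds about 0.71, and d reaches 0.597 at r of about 0.86. For the past month, both starts are significant even at r = 0. The starting visit therefore matters for significance in one window and over part of the range of r.

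**Which visit the documents mean**

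- Table 2 gives the baseline label to the week 0 column and keeps Screen apart. The Safety Evaluations text also equates baseline with V1.
- The Project Design overview lists Screening and Baseline as separate assessment times.
- The Aim 2 analysis sentence covers change from baseline to 24 weeks in TRQ together with BPRS, MADRS, YMRS and CGI, handled as in Aim 1. A Table 2 footnote says BPRS is the only symptom scale taken at Screen. For MADRS, YMRS and CGI, baseline can therefore only be BL/V1, and the same word in the same sentence covers TRQ.
- The EKG, laboratory and demographic items called baseline have no BL/V1 value. They show loose wording, but not a rival meaning for a measure taken at both visits.

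**The case for a change.** The strongest case for a change is that no sentence defines the TRQ baseline, the study is unblinded, and interim results may be presented while it runs, so the choice ought to be closed in advance. If the pilots' Screen-to-Baseline past-week fall recurred and nothing changed afterwards, a Screen-based test with 24 completers would be significant with probability 0.86, 0.95 and above 0.99 at r = 0.3, 0.5 and 0.7. Adherence barriers are assessed only at Screen and V7, so Aim 4 barrier change has to start at Screen. Naming the visit would take a sentence.

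Part of this stands. The definition is missing, the 0.60 has no stated contrast or window, and a Screen start would inflate the change. Three things weaken it.

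- The inflation arises only if analysts pass over the column labelled baseline in favour of the screening value. The barrier schedule concerns a different measure.
- The small past-week effect from Baseline depends on the assumed r. If the Table 1 p-values come from two-sided paired t-tests, which is not stated, past-month p = .002 at N = 25 implies d of about 0.69. That fits a Baseline start at r of about 0.52, whereas a Screen start would need r of about −0.25. Past-week p = .001 at N = 26 implies d of about 0.73, which needs r of about 0.90 from Baseline or −0.05 from Screen, so that row settles nothing.
- Table 1 rests on 26 and 25 of 60 patients and does not say that its columns share the same patients, so 23.7 may not be a paired change. The Study 1 figure of 46% is compared with two-study values, because that study's own Screen and Baseline values are not shown.

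**Conclusion.** The concern does not call for a change. It identifies a missing definition that analysts would fill correctly from the plan itself: the TRQ change starts at BL/V1, and Screen serves eligibility. On that reading the primary test already leaves out change before the first injection and CAE session, and the power figure of 0.597 is right. Table 1 has a Baseline column, so Aim 3 can be computed from the matching visit.

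The pilot falls before Baseline (71% past week, 40% past month) are a sound reason not to measure from Screen, but the plan does not say it will. The wrong choice could alter significance only for the past-week window and only if r is below about 0.71. This rests on pilot means from patients with schizophrenia or schizoaffective disorder, 24 completers and an assumed correlation. The unnamed recall window is a separate matter, and settling the starting visit would not resolve it. Reporting the Screen-to-BL/V1 change as well would be descriptive and would alter no result.
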